#### Pre-dose:

Only  $^{177}\text{Lu}$ -edotreotide group:

- Hospital admission (according to discretion of investigator and local regulations)
- Sub-study A: Repeated Full Dosimetry Imaging only: Transmission scan and blank scan or if available at the site whole body low dose CT scan. For further details see Day 0 (Section 7.3.1.1).

Only for everolimus group:

- Ambulatory visit, beginning pre-dose and ending approximately 3 h post-dose when all examinations and procedures are completed for day 90

Both treatment groups:

- Physical examination
- Vital signs
- Clinical laboratory tests
  - Haematology
  - Serum chemistry and clotting parameters
  - Urinalysis
- Tumour serum biomarker tests

- Pregnancy test
- 12-Lead ECG
- EORTC QLQ-C30 and GI.NET21
- Concomitant medications and SSA medications continuously
- Adverse events
- Evaluation of tumour response: native liver and contrast-enhanced liver and 3 regional (pelvis, abdomen, thorax) MRI or CT, baseline method to be adhered to

**Treatment:**

Lu-edotreotide group:

- Pre-medication with amino acid solution (see Section 6.1.3)
- Infusion/injection of undiluted Lu-edotreotide (dose D 2) over 10 to 20 min according to locally established practice

Everolimus group:

- Continuation of everolimus administration, 10 mg orally once daily
- Everolimus patients receive their diary

**Post-Treatment (only Lu-edotreotide group):**

Prior to Imaging:

- Vital signs immediately after end of infusion and 6 h ± 1 h post start of infusion
- Serum chemistry 5 h ± 1 h post start of infusion
- Concomitant medications and SSA medications continuously
- Adverse events continuously

Imaging:

- *Sub-study A: Repeated Full Dosimetry Imaging only: Lu whole body planar imaging immediately after vital signs assessment (approx. 0.5 h ± 0.25 h) and 6 h ± 1 h post start of infusion*

Post-imaging urine and blood samples (Sub-study C only)

The following samples will be collected only if Sub-study C is performed during the second Lu-edotreotide treatment cycle:

- Urine will be collected from all voids beginning immediately post-dose to 1 hour, and in intervals of 1-6 and 6-24 hours post-injection
- Blood samples of 1 mL, each will be drawn from a site on the lower arm below the amino acid infusion site, and opposite the arm receiving the infusion of Lu-edotreotide at 0 min, 10 min, 30 min, 1 h, 3 h, and 6 h post-injection (see Section 8.2.2.5).

#### 7.3.3.2 Day 91 (only $^{177}\text{Lu}$ -edotreotide group)

##### Prior to Imaging:

- Vital signs 24 h  $\pm$  3 h post start of infusion
- Blood sample serum chemistry 24 h  $\pm$  3 h post start of infusion
- Concomitant medications and SSA medications continuously
- Adverse events continuously

##### Imaging:

- Sub-study A: Repeated Full Dosimetry Imaging only:  $^{177}\text{Lu}$  whole body planar imaging 24 h  $\pm$  3 h post start of infusion.
- $^{177}\text{Lu}$  abdominal SPECT/CT imaging 24 h  $\pm$  3 h post start of infusion

##### Post-imaging urine and blood samples (Sub-study C only)

The following samples will be collected only if Sub-study C is performed during the second  $^{177}\text{Lu}$ -edotreotide treatment cycle:

- Urine sampling interval from 6-24 hours post-dose ends and next sampling interval from 24-48 hours post-dose starts
- Blood sample for dosimetry will be taken at 24 h  $\pm$  3 h post-injection

#### 7.3.3.3 Day 92 (only Sub-study C in $^{177}\text{Lu}$ -edotreotide group)

The following samples will be collected only if Sub-study C is performed during the second  $^{177}\text{Lu}$ -edotreotide treatment cycle:

- Urine sampling ends at 48 h ( $\pm$  3 h) post start of infusion
- Blood sample for dosimetry will be taken at 48 h  $\pm$  3 h post-injection

#### 7.3.3.4 Day 93 (only $^{177}\text{Lu}$ -edotreotide group)

##### Prior to Imaging:

- Vital signs 72 - 96 h ( $\pm$  3 h) post start of infusion
- 12-Lead ECG 72 - 96 h ( $\pm$  3 h) post start of infusion
- Concomitant medications and SSA medications continuously
- Adverse events continuously

Patients randomised to  $^{177}\text{Lu}$ -edotreotide group will receive bi-weekly safety controls for 8 weeks following  $^{177}\text{Lu}$ -edotreotide administration including haematology.

Imaging:

- Sub-study A: Repeated Full Dosimetry Imaging only:  $^{177}\text{Lu}$  whole body planar imaging 72-96 h post start of infusion
- Discharge of patients in the morning after day 93 or later, according to discretion of investigator and local regulations

An optional  $^{177}\text{Lu}$  whole body planar imaging for Sub-study A 7 days post end of infusion may be performed at investigator's discretion.

The following sample will be collected only if Sub-study C is performed during the second  $^{177}\text{Lu}$ -edotreotide treatment cycle: 1 mL blood sample for dosimetry will be taken 72 h  $\pm$  12 h post-injection.

#### **7.3.3.5 Day 97: Sub-study C Only**

The following sample will be collected only if Sub-study C is performed during the second  $^{177}\text{Lu}$ -edotreotide treatment cycle: 1 mL blood sample for dosimetry will be taken 7 days  $\pm$  12 h post-injection.

#### **7.3.4 Month 4 and Month 5**

The visits have to be performed at day 120 and 150 with  $\pm$  7 days window calculated from day 0. The examinations and procedures to be performed are identical to month 1.

#### **7.3.5 Month 6**

The visit has to be performed at day 180 with  $\pm$  14 days window calculated from day 0. Days 181 and 183 will be calculated from the actual day 180 visit date.

All patients will undergo a  $^{99\text{m}}\text{Tc}$ -MAG3 renal scintigraphy.

All further examinations and procedures to be performed at month 6 are identical to month 3. Pre-dose procedures may be performed within 7 days before Day 180 for both treatment groups. Investigations should be performed as close to PRRT or dosing as possible and as clinically appropriate.

If Sub-study C is to be performed during the third  $^{177}\text{Lu}$ -edotreotide treatment cycle, the urine and blood samples for Sub-study C are to be collected as described for month 3.

#### **7.3.6 Month 7 and Month 8**

The visits have to be performed at day 210 and 240 with  $\pm$  7 days window calculated from day 0. The examinations and procedures to be performed are identical to month 1.

**7.3.7 Month 9**

The visit has to be performed at day 270 with  $\pm 14$  days window calculated from day 0. Days 271 and 273 will be calculated from the actual day 270 visit date.

Patients randomised to  $^{177}\text{Lu}$ -edotreotide will receive dose D4 at day 270 provided that the kidney function allows administration (see Sections 3.1 and 5.4.3.2).

All further examinations and procedures to be performed at month 9 are identical to month 3. Pre-dose procedures may be performed within 7 days before Day 270 for both treatment groups. Investigations should be performed as close to PRRT or dosing as possible and as clinically appropriate.

If Sub-study C is to be performed during the fourth  $^{177}\text{Lu}$ -edotreotide treatment cycle, the urine and blood samples for Sub-study C are to be collected as described for month 3.

**7.3.8 Month 10 and Month 11**

The visits have to be performed at day 300 and 330 with  $\pm 7$  days window calculated from day 0. The examinations and procedures to be performed are identical to month 1.

**7.3.9 Second Year**

During the second year of the study, patients in the everolimus arm continue on everolimus, while patients in the  $^{177}\text{Lu}$ -edotreotide arm will not receive further PRRT treatment until diagnosis of progression. Study visits during the 2nd year take place on an out-patient basis in 3-monthly intervals (12, 15, 18, 21, 24, and 27 months after day 0, with  $\pm 21$  day time window). For the management of patients impacted by the follow-up extension, see Section 3.1. Examinations comprise physical examination, vital signs, blood sampling for laboratory and tumour markers, pregnancy test, EORTC QLQ questionnaire, recording of AEs and concomitant medication, morphological MRI/CT imaging at every second year visit, as well as 12-lead ECG and  $^{99\text{m}}\text{Tc}$ -MAG3 renal scintigraphy at months 12, 18, and 24 only. Morphological MRI/CT imaging and  $^{99\text{m}}\text{Tc}$ -MAG3 renal scintigraphy should be performed within 7 days prior to the study visit, in order for the results to be available at the time of the visit. Pregnancy tests for the following months without visits at the study centre will be handed out to the patients at every visit. Blood-sampling can be performed up to 72 hours prior to each visit according to local practice and as clinically appropriate. Pregnancy tests are to be repeated monthly during year 2 until EOS. Everolimus patients continue to receive their patient diary at every visit.

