## **5.2 Treatment Assignment and Randomisation**

All successfully screened patients will be randomised in a 2:1 fashion, to receive:

- a) Lu-edotreotide (at most four Lu-edotreotide doses, administered 3-monthly) or
- b) Everolimus (Afinitor®, administered daily).

Randomisation will follow a confidential, pre-defined scheme under direct control of the Study Data Management. Details of treatment assignment procedure, from the initial request down to the delivery of the requested IMP will be described in the IMP-Management Plan.

Stratified randomisation, using four randomisation lists, will be used to ensure in both study arms a balanced frequency of GE-NET patients vs. P-NET patients and a balanced frequency of patients naive to medical treatment (1st line patients) vs. patients who have received prior medical therapies (2nd line patients). Prior therapies may include chemotherapy, SSA, targeted therapy (e.g. sunitinib), and others; the types of prior therapies will have to be recorded in the CRF (see also Section 9.2.3.2). Furthermore, inclusion of an equal number of GE-NET and P-NET will be attempted, but any ratio will also be acceptable as long as it allows meaningful subgroup analysis.

Randomisation should be performed as soon as all necessary information for patient eligibility from screening assessments is available. Start of treatment should commence as soon as possible after randomisation, e.g. on the day of randomisation (everolimus group). In the Lu-edotreotide group, the study drug needs to be ordered on the day of randomisation. The first dose of Lu-edotreotide should be administered within 21 days of randomisation. In case of any delay, the site should check with the Sponsor via the site monitor and the reason for delay should be documented accordingly.

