As only standard  $^{177}\text{Lu}$ -edotreotide doses of  $7.5 \text{ GBq} \pm 0.7 \text{ GBq}$  are used in this study, dose modification will not be achieved by reducing the next planned dose, but by delaying the next treatment cycle up to a maximum of 4 weeks (week 16 (+ 2)). In such a situation, subsequent PRRT cycles and evaluations (except for evaluation of tumour response based on morphological imaging RECIST 1.1) will be performed in intervals of 90 ( $\pm 14$ ) days, calculated from the delayed PRRT cycle. In case toxicity has not recovered by week 16, a patient cannot receive further PRRT cycles, but will remain in the study.

Following the second occurrence of DMT, the patient is excluded from further treatment, but will remain in the study.

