If randomisation reveals assignment to the everolimus arm, treatment should be initiated as soon as possible (preferably no later than 21 days after randomisation). The randomisation visit can then be taken as day 0 of treatment if all required pre-dose examinations were performed on the same day.

If a patient is a screen failure, the following information is to be collected in the electronic case report for (eCRF):

- Date of informed consent
- Date of the screening visit
- Demography (see Section 8.1.1)
- Inclusion/exclusion criterion number not met
- Serious adverse event, if applicable
- EOS page of eCRF is to be completed with reason "Screen Failure"

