**7.3.10 End of Study (EOS)**

The EOS visit will be performed 30 months from day 0, or after establishment of definitive disease progression, whatever occurs earlier (see Section 8.2.4). Study patients who experience disease progression established prior to the next planned visit are required to complete the EOS visit. For the management of patients impacted by the follow-up extension, see Section 3.1.

The following examinations and procedures will be performed:

- Physical examination

- Vital signs
- Clinical laboratory tests
  - Haematology
  - Serum chemistry and clotting parameters
  - Urinalysis
- Tumour serum biomarker tests
- Pregnancy test
- 12-Lead ECG
- EORTC QLQ-C30 and GI.NET21
- Concomitant medications and SSA medications
- Adverse events
- MRI (CT) evidencing radiological tumour progression by RECIST 1.1: native liver and contrast-enhanced liver and 3 regional (pelvis, abdomen, thorax) MRI or CT, baseline method to be adhered to - not to be repeated in case of progression
- 99mTc-MAG3 renal scintigraphy

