### **9.2.1 Primary Variable**

#### Progression-free survival

Progression-free survival will be determined starting from randomisation until the date of an event (PD by RECIST 1.1 or death). For the primary analysis, any withdrawal (or drop-out) before EOS visit will be censored. Patients who have not shown progression at the end of the study will also be censored.

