2.2.1 Primary endpoint

The primary endpoint is

- progression-free survival (PFS)

determined as time elapsed between randomisation and the date of first objective report of tumour progression (evaluated by RECIST criteria, 1.1), or death.

For the purpose of the main confirmatory PFS analysis, central blinded image readings in duplicate, with appropriate adjudication in case of discordance will be used. Local assessments will be presented in sensitivity analysis.

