3.4 Study Variables

3.4.1 Primary Variable

Progression-free survival

Progression-free survival will be determined starting from randomisation until the date of an event (PD or death). For the primary analysis, any withdrawal (or drop-out) before EOS visit at month 30 will be censored. Patients who have not shown progression at the end of the study (30 months) will also be censored.

In more details, the following rules will be applied for the main PFS analysis:

ITM-LET-01	Statistical Analysis Plan
------------	---------------------------

Table 1: PFS analysis rules

Situation	Date of Progression or Censoring	Outcome
Tumour progression or death	Earliest date of PD or death	Event (PD or Death)
No tumour progression and not death	Date of last adequate* radiological assessment	Censored
Unless:		
No baseline radiological tumour assessment	Date of randomisation	Censored
No adequate post-baseline radiological assessment and date of death, if any, is after 2 or more scan intervals following randomization**	Date of randomisation	Censored
New anticancer treatment started prior to tumour progression or death (whichever is earlier)	Date of the last adequate radiological assessment prior to start of new anticancer treatment or date of randomization (whichever is later)	Censored
Tumour progression or death documented immediately after 2 or more consecutive missing scan** following last adequate radiological tumour assessment or randomization (whichever is later).	Date of last adequate radiological tumour assessment or date of randomisation (whichever is later).	Censored

Table footnotes:

**Adequate radiological tumour assessment refers to an assessment with one of the following responses: CR, PR, SD, or PD.*

***The interval is higher than 2 times the maximal protocol scheduled RECIST 1.1 assessment interval (i.e. >222 days = 2*(90+21))*

For primary endpoint (PFS) main analysis, post-randomisation tumour assessment based on blinded central review compare to baseline will be used.

Where appropriate, sensitivity analyses will explore the impact of the chosen approaches and data issues observed during the blind review on the study results. These could include but not limit to:

- Blinded central RECIST 1.1 evaluation (main analysis) vs. Local RECIST assessments
- Applied main PFS censoring rules (main analysis, see Table above) vs. different approaches (e.g. next scheduled assessment date instead of date of radiological

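### PFS is timed from randomisation but the scheduled scans are timed from first dose; if the start lag is longer in the PRRT arm, which is likely but not certain, the log-rank test is biased towards PRRT

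*Protocol*

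**What the plan says.** **Time origin.** SAP 2.2.1 defines PFS as "determined as time elapsed between randomisation and the date of first objective report of tumour progression", or death. Protocol 9.2.1 and SAP 3.4.1 also start the clock at randomisation ("Progression-free survival will be determined starting from randomisation until the date of an event (PD by RECIST 1.1 or death"; "Progression-free survival will be determined starting from randomisation until the date of an event (PD or death").

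**Scan schedule.** Imaging visits at months 3, 6 and 9 are counted from day 0 with a window of ±14 days (Protocol 7.3.3.1, 7.3.5, 7.3.7). From month 12 they run "in 3-monthly intervals (12, 15, 18, 21, 24, and 27 months after day 0", with ±21 days. For the last visit, "The EOS visit will be performed 30 months from day 0". Scans may precede the visit by up to 7 days. Day 0 is the day of first treatment (Protocol 7.3.1.1).

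**Time from randomisation to day 0.**
- Protocol 5.2: "Start of treatment should commence as soon as possible after randomisation, e.g. on the day of randomisation (everolimus group".
- Protocol 7.2.1, for everolimus: "The randomisation visit can then be taken as day 0 of treatment if all required pre-dose examinations were performed on the same day". The same section and Table 2 footnote V prefer an everolimus start within 21 days.
- 177Lu-edotreotide is ordered on the day of randomisation (Protocol 5.2) and produced for each order (Protocol 5.1.3). Its first dose has a 21-day target; longer delays need sponsor contact and documentation.

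**Safeguards.** When a PRRT cycle slips for toxicity, Protocol 5.4.3.2 moves later evaluations with it, "except for evaluation of tumour response based on morphological imaging RECIST 1.1". There is no matching rule for the initial lag. SAP 3.4.1 gives an open list of PFS sensitivity analyses, none of which re-anchors the scans. Its option of using the next scheduled assessment date concerns progression found between scheduled scans and keeps the day-0 schedule.

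**The concern.** Radiological progression is dated at the scan that shows it, so PFS events cluster at scan dates. The log-rank test depends only on the order of events. If one arm's scan grid sits two or three weeks to the right on the randomisation clock, its events in each scan round tend to fall just after the other arm's, even when true progression times are identical. If PRRT patients wait longer for their first dose, this favours PRRT in the confirmatory test at every look.

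The exploratory 2-year PFS rate is exposed as well. For a patient dosed 21 days after randomisation, the month-24 scan is nominally due 21 days after the 24-month point at which the Kaplan-Meier curve is read.

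**Working it through.** **1. The plan's own figure.** SAP 4: 180 events, 1:2 allocation, HR 11/17 = 0.6471, two-sided 5%, 80% power.
- Schoenfeld: z = |ln 0.6471| × √(180 × 1/3 × 2/3) − 1.96 = 0.4353 × 6.325 − 1.96 = 0.793, power 78.6%.
- With the stated 68/112 event split: 0.4353/√(1/68 + 1/112) − 1.96 = 0.872, power 80.8%.

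The plan's figure is reproduced to within 2 points. The documents give no figure for the lags or their effect.

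**2. The two grids in days from randomisation (first-year visits).**
- Lag 0: 90, 180, 270.
- Lag 14: 104, 194, 284.
- Lag 21: 111, 201, 291.

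Only the first interval is longer (90 against 111 days at lag 21); later intervals are equal, but the whole grid stays displaced.

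**3. Simulation under no true effect.** From the documents: 100 against 200 patients, median 11 months (used in both arms), 3-monthly scans to month 30, visit windows ±14 days (±21 from month 12), scan 0-7 days before the visit. Assumed: exponential progression, the lags shown, one unstratified log-rank test at 1.96, no interim looks, no deaths or off-schedule scans. Model A has no dropout; model B has about 15% dropout and about 240 events. A false win is z < −1.96 in favour of PRRT (nominal 2.5%).

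| Lag in days, everolimus / PRRT | Model A: false win, HR | Model B: false win, HR |
|---|---|---|
| 0 / 7 | 4.9%, 0.97 | 5.1%, 0.95 |
| 0 / 14 | 7.5%, 0.95 | 7.5%, 0.93 |
| 0 / 21 | 8.4%, 0.93 | 8.5%, 0.92 |
| 0-7 / 7-21 | 6.1%, 0.95 | not run |
| 0-14 / 7-21 | not run | 5.0%, 0.96 |
| 0-21 / 10-21 | 4.1%, 0.97 | not run |
| 0-21 / 7-21 | not run | 3.9%, 0.98 |
| 0-21 / 0-21 | 3.0%, 1.00 | 2.5%, 1.00 |

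With both grids anchored at randomisation, model A gives HR 1.00 and a false-win rate of 2.5-3%. Model B used 2,000 trials per row, so a 5% rate has a standard error of √(0.05 × 0.95/2000) = 0.5 points.

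**4. Under the design effect (11 against 17 months, model A).** The apparent HR is 0.647 with both grids anchored at randomisation and about 0.61 for lags of 0 and 21 days.

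**5. Why a small delay matters.** For 0 against 21 days with no true effect, the mean delay from true progression to detection is 47.2 against 49.7 days, a difference of 2.5 days. The observed medians are 12.16 and 12.55 months, about 0.4 months apart. The false wins come from the displaced grid; the mean delay itself is small.

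**The case against.** A reader might infer that progression is systematically dated later in the PRRT arm. The documents do not establish that. Both arms have the same soft 21-day target. A same-day everolimus start is an example, and counting the randomisation visit as day 0 depends on all pre-dose examinations being done that day. SAP 3.1 places randomisation at day −28 to −1 without separating the arms, so a gap is foreseen for everolimus too. With equal lags the bias disappears. This objection stands, and it makes the point conditional. It does not remove it: only the PRRT dose has to be ordered and made after randomisation, so equal lags are the less likely case.

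A reader might also take 21 days as the longest possible PRRT lag, or think each PRRT progression is dated three weeks late. Neither follows. The 21 days are a target that may be exceeded, and the mean detection delay grows by only about 1 to 2.5 days in the 0 against 7-21 day cases.

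The simulations also leave out deaths, which have exact dates, and imaging on clinical suspicion, which the protocol allows at any time. If 20% of events fell off the scan grid (an assumption), the 0 against 21 day case would drop to about 6%. The effect is then smaller but still above nominal.

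Finally, the synopsis planned recruitment to end in 2021 and the study in 2024, so re-anchoring may affect few scans. That is fair, and it makes the added analysis the main remedy.

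**Conclusion.** The point holds in conditional form. The PFS clock and the scan schedule have different origins, the supply route makes a longer lag likely in the PRRT arm, and no named analysis addresses it. If the PRRT lag is longer, the confirmatory log-rank test is biased towards PRRT.

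Under the assumed lags and the protocol's windows, the false PRRT win rate is about 5-9% with HR about 0.92-0.97 for 0 against 7-21 days. It is about 4% with HR about 0.98 for overlapping lags of 0-21 against 7-21 days, and there is no bias when lags match. These figures rest on exponential progression, a single look and events seen only at scheduled scans, so they show direction and order of size and are not a forecast for the three-look design.

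A reader might conclude that a positive PFS result could not be trusted. The documents do not support that: the actual lags are unknown, and at the design effect the distortion is from 0.647 to about 0.61 even for 0 against 21 days. The point is worth acting on because the likely direction favours the sponsor's product and the remedy is cheap.

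**What to change.** 1. **Scans still to come:** in Protocol 7.3, 8.2.1.2 and Tables 1-2, count the MRI/CT schedule from randomisation in both arms. Dosing and safety visits stay on day 0.
2. **Scans already acquired:** add to SAP 3.4.1 a named interval-censored PFS sensitivity analysis. Progression is placed between the last progression-free scan and the scan showing it, both measured from randomisation, and deaths keep their exact dates.
3. **Companion analysis:** a log-rank test on nominal visit times (the same in both arms) or grouped by scan number.
4. **Reporting:** tabulate randomisation-to-first-dose and randomisation-to-scan intervals by arm, so that the reader can see whether the condition is met.

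**Cost.** A small amendment and a few lines of SAP text, with no extra scans or patients. In the PRRT arm, scans and dosing visits may be up to about 3 weeks apart; the trial team would have to square this with the present rule that pre-dose procedures stay close to dosing. The nominal-visit analysis has more ties and is slightly conservative when the PRRT lag is longer (HR about 1.02-1.05 under no effect), so it should accompany the interval-censored analysis and not replace it.
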